11.5.2. Adverse Event and Device Deficiency Reporting Requirements

Regulatory reporting of AEs and DDs will be recorded and reported according to local requirements. It is the responsibility of the Investigator and the sponsor to abide by the AE reporting requirements stipulated by local law and the study site's IRB/EC. Refer to [Table 9: Safety Reporting Requirements](#) for more details related to reporting timelines.

Medtronic Business Restricted

Table 9: Safety Reporting Requirements

SAE	
Investigator shall submit to:	
Medtronic	
Europe: To the sponsor in acceptable timely conditions, but not later than within 3 calendar days after investigational site study personnel's awareness of the event or of new information in relation with an already reported event.
 
All other geographies: Report to the sponsor, without unjustified delay, all serious adverse events

IRB/EC	All geographies: Submit to IRB/EC as per local requirement.
Regulatory Authority	All geographies: As per local requirement.
Sponsor shall submit to:	
IRB/EC	All geographies: Submit to IRB/EC as per local requirement.
Regulatory Authority	All geographies: Reporting timeframe as per local requirement.
SADE	
Investigator shall submit to:	
Medtronic	
Canada: SAEs on the patient, the user or any other person must be reported to the regulator and to the Sponsor within 72 hours after it comes to the attention of the qualified investigator.
 
Europe: To the sponsor in acceptable timely conditions, but not later than within 3 calendar days after investigational site study personnel's awareness of the event or of new information in relation with an already reported event
 
US: Report to the sponsor, without unjustified delay, all serious adverse device events

IRB/EC	All geographies: Submit to IRB/EC as per local requirement.
Regulatory Authority	
Canada: SAEs on the patient, the user or any other person must be reported to the regulator and to the Sponsor within 72 hours after it comes to the attention of the qualified investigator.
 
All other geographies: As per local requirement.

Sponsor shall submit to:	
IRB/EC	All geographies: Submit to IRB/EC as per local requirement.
Regulatory Authority	All geographies: Reporting timeframe as per local requirement.
UADE	
Investigator shall submit to:	
Medtronic	US: As soon as possible, but in no event later than 10 working days after the investigator first learns of the effect.
IRB/EC	US: As soon as possible, but in no event later than 10 working days after the investigator first learns of the effect.
Regulatory Authority	US: As per local requirement.
Sponsor shall submit to:	
IRB/EC	US: Submit to IRB/EC as per local requirement.

Medtronic Business Restricted

Regulatory Authority	US: Reporting timeframe as per local requirement.
USADE	
Investigator shall submit to:	
Medtronic	
Canada: USADEs on the patient, the user or any other person must be reported within 72 hours after it comes to the attention of the qualified investigator.
 
Europe: To the sponsor in acceptable timely conditions, but not later than within 3 calendar days after investigational site study personnel's awareness of the event or of new information in relation with an already reported event.

IRB/EC	
Canada: Submit to IRB/EC as per local requirement.
 
Europe: Submit to IRB/EC as per local requirement.

Regulatory Authority	
Canada: USADEs on the patient, the user or any other person must be reported within 72 hours after it comes to the attention of the qualified investigator.
 
All other geographies: As per local requirement.

Sponsor shall submit to:	
IRB/EC	All geographies: Submit to IRB/EC as per local requirement.
Regulatory Authority	All geographies: Reporting timeframe as per local requirement.
Deaths	
Investigator shall submit to:	
Medtronic	All geographies: Without unjustified delay after learning of a subject's death, regardless of whether the death is related to the device system or therapy.
IRB/EC	
Canada: All subject deaths must be reported to the EC as soon as possible, but no more than 72 hours of learning of a subject's death, regardless of whether or not the death is related to the device system or therapy.
 
All other geographies: Submit to IRB/EC as per local requirement.

Regulatory Authority	All geographies: As per local requirement.
Sponsor shall submit to:	
IRB/EC	All geographies: Submit to IRB/EC as per local requirement.
Regulatory Authority	All geographies: Reporting timeframe as per local requirement.
All other AEs	
Investigator shall submit to:	
Medtronic	All geographies: Submit in a timely manner after the Investigator first learns of the event
IRB/EC	All geographies: Submit to IRB/EC as per local requirement.
Regulatory Authority	All geographies: As per local requirement.
Sponsor shall submit to:	
IRB/EC	All geographies: Submit to IRB/EC as per local requirement.
Regulatory Authority	All geographies: Reporting timeframe as per local requirement.

Medtronic Business Restricted

Investigational DDs with SADE potential	
Investigator shall submit to:	
Medtronic	
Canada: DDs that have resulted in any of the consequences characteristic of an SAE on the patient, the user or any other person or could do so were it to reoccur must be reported to the regulator and the Sponsor within 72 hours after it comes to the attention of the qualified investigator.
 
Europe: To the sponsor in acceptable timely conditions, but not later than within 3 calendar days after investigational site study personnel's awareness of the event or of new information in relation with an already reported deficiency.
 
US: Reporting timeframe as per local requirement

IRB/EC	All geographies: Submit to IRB/EC as per local requirement.
Regulatory Authority	
Canada: DDs that have resulted in any of the consequences characteristic of an SAE on the patient, the user or any other person or could do so were it to reoccur must be reported to the regulator and the Sponsor within 72 hours after it comes to the attention of the qualified investigator.
 
All other geographies: As per local requirement.

Sponsor shall submit to:	
IRB/EC	All geographies: Submit to IRB/EC as per local requirement.
Regulatory Authority	All geographies: Reporting timeframe as per local requirement.
All other Device Deficiencies	
Investigator shall submit to:	
Medtronic	All geographies: Submit in a timely manner after the Investigator first learns of the device deficiency
IRB/EC	All geographies: Reporting timeframe as per local IRB/EC requirement.
Sponsor shall submit to:	
IRB/EC	All geographies: Submit to IRB/EC as per local requirement.
Regulatory Authority	All geographies: Reporting timeframe as per local requirement.

IRB/EC and Competent Authority (CA) reporting must be completed in accordance with the local reporting policies of the governing IRB/EC and CA.

11.6. Subject Death

The investigator must notify Medtronic and the governing IRB/EC (as required) without unjustified delay after learning of a subject's death, regardless of whether the death is related to the device system or therapy. The Investigator should also attempt to determine, as conclusively as possible, whether such deaths are related to the device, procedure or therapy.

Medtronic Business Restricted

Any subject death will be reported on the Adverse Event and Study Exit eCRF accordingly. For the Adverse Event eCRF, the death should not be reported as a diagnosis of the event, rather as an outcome of the event which led to death.

If an autopsy is conducted, a copy of the de-identified report will be provided to Medtronic. Medtronic requests that all device system components that were being used at the time of the death be returned to Medtronic for analysis per [Section 6.10](#), Product Return.

A copy of the death certificate, if available and allowed by state/local law, should be sent to the Medtronic clinical study team. When a death occurs in a hospital, a copy of the death summary report and all relevant hospital records, if available should be sent to the Medtronic clinical study team. When the death occurs at a remote study site, it is the investigative study site's responsibility to attempt retrieval of information about the death. If a death certificate or summary report are unavailable, and investigator summary of the death is acceptable. Additionally, device disposition information should be updated.

In summary, the following data will be collected:

- Date of death
- Detailed description of death
- Cause of death
- Relatedness to system and procedure
- Device interrogation information/reports (if available)
- Device disposition information
- Death summary/hospital records (if available and allowed by state/local law)
- Autopsy report (if available and allowed by state/local law)
- Death certificate (if available and allowed by state/local law)

11.7. Product Complaint Reporting

Product complaint reporting and vigilance reporting are applicable and AEs related to any market-released device during the study must be reported. The reporting of product complaints is not part of the study and should be done in addition to the AE reporting requirements. Refer to local regulations for reporting requirements.

Product Complaint: Any written, electronic or oral communication that alleges deficiencies related to the identity, quality, durability, reliability, safety, effectiveness or performance of a medical device that has been placed on the market.

It is the responsibility of the investigator to report all product complaint(s) associated with a medical device distributed by Medtronic, regardless of whether they are related to intended use, misuse or abuse of the product. Reporting must be done immediately and via the regular channels for market-

Medtronic Business Restricted

released products. The reporting of product complaints by the clinical team must be done according to the local Standard Operating Procedures. Medtronic will notify the RAs (e.g. CA) as applicable for the following incidents immediately upon learning of them and is not limited to AEs and DDs only:

- Any malfunction or deterioration in the characteristics and/or performance of a device, as well as any inadequacy in the labeling or instructions for use which led or might have led to the death or serious deterioration in the state of health of a patient, user, or other person.
- Any technical or medical reason resulting in withdrawal of a device from the market by the manufacturer.
- Any serious deterioration in the state of health, including:
 - Life-threatening illness or injury
 - Permanent impairment of a body function or permanent damage to a body structure
 - A condition necessitating medical or surgical intervention to prevent permanent impairment of a body function or permanent damage to a body structure

12. Data Review Committees

12.1. Data Monitoring Committee

The main objective of the ADAPT-PD Trial Data Monitoring Committee (DMC) is to advise Medtronic regarding the continued safety of study subjects and those yet to be recruited to the study; and to ensure the validity and scientific merit of the study.

The DMC will be external to Medtronic and independent of the study investigators. The physician members will have specialties appropriate to the therapeutic area and all members will meet requirements established in the DMC charter.

The DMC will be responsible for:

- Assessing the progress of the ADAPT-PD trial, including the accumulation of safety data
- Evaluating study conduct (eg, data quality) for the impact on validity and scientific merit of the ADAPT-PD Trial
- Considering factors external to the study when relevant information becomes available, such as scientific or therapeutic developments that may have an impact on the safety of the participants or the ethics of the study
- Recommending to the sponsor whether to continue, modify, or stop the study

Medtronic personnel (eg, statistician, Medtronic study management team) may facilitate the DMC meetings, provide study progress updates and answer questions. Medtronic personnel will not be voting members.

Medtronic Business Restricted

The DMC Charter will define the DMC processes for member selection, meeting frequency, roles and responsibilities, procedures, and record keeping. The DMC may call additional meetings whenever there are concerns regarding any aspect of the study.

12.2. Clinical Events Committee

This study will utilize a Clinical Events Committee (CEC) to review and adjudicate all reportable stimulation/therapy, procedure and device related (S)AEs and deaths for seriousness and relationship to the procedure, device, and therapy/stimulation using the definitions provided in [Section 11.4](#). The CEC Charter will define the CEC processes for member selection, meeting frequency, roles and responsibilities, procedures, and record keeping.

Prior to making a final adjudication decision, the CEC may request clarification and/or additional information from the principal investigator who reported the event. If the conclusion of the review differs from the principal investigator's assessment, both opinions will be reported back to the investigator and noted in the final study report. Incidence rates will be tabulated using the final CEC determination.

13. Statistical Design and Methods

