Relationship of Adverse Events	
The relationship of an adverse event will be classified as device-related, therapy/stimulation-related, procedure-related, related to the disease under study, and/or related to an underlying condition or disease based on the following definitions:
 
 • Device Related: An adverse event that results from the presence or performance (intended or otherwise) of the DBS system or any of the DBS system components • Procedure Related: An adverse event that occurs due to any procedure related to the surgical modification, or explant of the DBS system or any of the DBS system components. • Therapy/Stimulation Related: An adverse event related to therapy delivery by the DBS system (i.e. stimulation). Normally therapy-related events resolve when the device is turned off or reprogrammed. • Related to the disease under study: An adverse event that is caused by Parkinson's disease • 
Each of the relatedness classifications will be assessed for causality using five different levels of causality based on the following definitions:
 
 • Not Related: relationship to the device, comparator or procedures can be excluded when: 
 ○ the event has no temporal relationship with the use of the investigational device or the procedures related to application of the investigational device; ○ the serious event does not follow a known response pattern to the medical device (if the response pattern is previously known) and is biologically implausible; ○ the discontinuation of medical device application or the reduction of the level of activation/exposure - when clinically feasible – and reintroduction of its use (or increase of the level

Medtronic Business Restricted

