11.5.1. Adverse Event and Device Deficiency Classification

All AE and DD will be reviewed by a Medtronic representative. AEs will be classified according to the definitions provided.

Upon receipt of AE/DD at Medtronic, a Medtronic representative will review the AE/DD for completeness and accuracy and when necessary, will request clarification and/or additional information

Medtronic Business Restricted

from the Investigator. Medtronic will utilize MedDRA for Regulatory Activities, to assign a MedDRA term for each AE/DD based on the information provided by the investigator. Copies of de-identified source documentation regarding an adverse event or device deficiency (eg, clinician notes or summaries) will be provided to Medtronic upon request.

Regulatory reporting of AEs and DDs will be completed according to local regulatory requirements. Refer to [Table 9](#) for a list of required investigator and Medtronic reporting requirements and timeframes. It is the responsibility of both to abide by any additional AE reporting requirements stipulated by the IRB/EC responsible for oversight of the study.

For emergency contact regarding a UADE, USADE, SAE and/or SADE, contact a study representative immediately (refer to the study contact list provided in the study site's study documents binder/investigator site file or refer to the Sponsor contact information provided on the title page).

AEs will be classified according to the standard definitions as outlined below in [Table 8](#):

Table 8: Event Classification Responsibilities

What is Classified	Who Classifies	Classifications
Relatedness*	
InvestigatorSponsor	
Relationship to the:
ProcedureDeviceTherapy/StimulationDisease under study
USADE/UADE potential	Sponsor	USADE/UADE
Seriousness	Investigator	SAE, DD with SADE potential
	Sponsor	SAE, DD with SADE potential
Diagnosis	Investigator	Based on presenting signs and symptoms and other supporting data
	Sponsor	MedDRA term assigned based on the data provided by investigator

**Adverse events that are classified as having a relationship of possible, probable or causal to the investigational device, procedure or therapy/stimulation are considered to be related to the investigational medical device and are classified as ADEs.*

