In addition, all ADEs and deaths will be reviewed and adjudicated (seriousness, relationship/causality) by an independent Clinical Events Committee. Refer to [Section 12.2](#).

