7.10 Safety Evaluation

The safety assessment is to characterize:

- Stimulation-related adverse events during the aDBS evaluation and the cDBS baseline phases.
- Serious adverse events, adverse events, and device deficiencies throughout the study.

Stimulation-related adverse events will be summarized during the cDBS Baseline and aDBS Evaluation Phases for all subjects, with tabulations individualized by aDBS mode in the Primary Cohort, by target site in the Primary Cohort, by lead type in the Primary Cohort, and the Directional Stimulation Cohort (DSAT analysis set). Summarized results from the Directional Stimulation Cohort will be provided as supporting analyses to the Primary Cohort results. In the Primary Cohort, if statistical comparisons of poolability across mode, lead type, and target site are accepted, overall tabulations will be provided as appropriate. To test for a difference in safety by target site (STN/GPi) and lead type, Fisher's exact test will be computed testing for differences between target sites and between lead type in the proportion

of subjects with a stimulation-related adverse event during the aDBS Evaluation Phase using data from both periods. [REDACTED]

[REDACTED]

[REDACTED]

[REDACTED]

A repeated measures logistic regression will be used to test for a difference between aDBS modes in the proportion of subjects with stimulation-related adverse events in the randomized subjects who enter the aDBS evaluation phase in the Primary Cohort. [REDACTED]

[REDACTED]

[REDACTED]

[REDACTED]

[REDACTED]

[REDACTED]

P-values >0.1 will be deemed as supporting the assumption of no target site, lead type, or mode effect, respectively, and the data will be considered poolable across the respective variable. If the p-value approaches statistical significance (defined as ≤ 0.1),¹ safety summaries will not be provided as a combined summary for that variable.

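### Non-fatal events first called unrelated on every axis do not go to the Clinical Events Committee, yet its verdict sets the incidence rates, so adjudication leans towards a lower stimulation-related rate

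*Protocol*

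**What the plan says.** Protocol 12.2 asks the CEC to "review and adjudicate all reportable stimulation/therapy, procedure and device related (S)AEs and deaths", and to do so "for seriousness and relationship to the procedure, device, and therapy/stimulation using the definitions provided in" Section 11.4. It then states: "Incidence rates will be tabulated using the final CEC determination". Where the CEC and the investigator differ, both opinions are noted in the final study report.

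Protocol 11.5.1 gives the same scope: "all ADEs and deaths will be reviewed and adjudicated (seriousness, relationship/causality) by an independent Clinical Events Committee". An adverse event counts as an adverse device effect (ADE) when it is "classified as having a relationship of possible, probable or causal to the investigational device, procedure or therapy/stimulation". The table headed "Table 8: Event Classification Responsibilities" assigns relatedness to the investigator and the sponsor, with no rule for disagreement between them.

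Protocol 11.4 grades each axis separately: "Each of the relatedness classifications will be assessed for causality using five different levels of causality". Possible and above count as related, and cases whose relatedness cannot be assessed are to be classed as possible.

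SAP 7.10 plans the analysis: "Stimulation-related adverse events will be summarized during the cDBS Baseline and aDBS Evaluation Phases for all subjects". That section does not mention the CEC.

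**The concern.** An independent committee should be able to correct the first relatedness call in both directions. Here its caseload depends on that call. False positives can be removed. False negatives among non-fatal events are never seen if they were called unrelated on all three axes.

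The first call is made by the investigator and the sponsor. Protocol 13.8 lists blinding of subjects only, so site staff know which therapy was running. Attribution is also a matter of judgement, because Parkinson's disease itself is a competing category in Protocol 11.4.

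Stimulation-related events in the cDBS Baseline and aDBS Evaluation Phases are the first safety item (Protocol 4.1.3 and 13.6). Their proportion also feeds the poolability tests by target site, lead type and mode in SAP 7.10.

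**Working it through.** **1. Which events can change status.** The entry gate is related to any of three axes (Protocol 11.5.1). The tabulated outcome is one axis, therapy/stimulation.

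| First call | Reaches CEC? | Possible effect on the stimulation-related rate |
|---|---|---|
| Possible or higher for stimulation | Yes | Down, or no change |
| Possible or higher for device or procedure only | Yes | Up, or no change |
| Death, not called stimulation-related | Yes | Up, or no change |
| Non-fatal, not related or unlikely on all three axes | No | None; cannot be corrected |

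If the sponsor's call alone is enough for referral, an event that only the sponsor calls related could also raise the rate above the investigator's. The documents do not say whether it is enough.

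The procedure route looks narrow. Procedure-related means surgical modification or explant (Protocol 11.4), and implant precedes enrollment (6.1.1). A subject with a system modification should be exited before randomization, or does not complete the evaluation periods after it (9.14).

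**2. The plan's own safety figure.** Protocol 13.2.4 states at least 95% probability that an event with a true rate of 10% is reported at least once in 30 subjects. The check is 1 − 0.9^30 = 0.9576, which agrees. As a yardstick, suppose a share q of such events is not tabulated as stimulation-related, at whichever step. The probability that the event appears under that label is 1 − (1 − 0.10 × (1 − q))^30:

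- q = 0.10: 94.1%
- q = 0.20: 91.8%
- q = 0.30: 88.7%

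Restoring 95% would take 32, 36 or 42 subjects respectively. The planned minimum of 36 completers covers the first two. The values of q are assumptions.

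**3. Direction of the adjudication effect (assumed counts).** Take 40 subjects, of whom 12 have an event first called stimulation-related: 12/40 = 30.0%.

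- 10% downgraded, none added: 10.8/40 = 27.0%.
- 20% downgraded, none added: 9.6/40 = 24.0%.
- Four other subjects have device- or procedure-only events, with no downgrades. One upgraded gives 13/40 = 32.5%; all four give 16/40 = 40.0%.
- The same four subjects, 20% downgraded and all four upgraded: 13.6/40 = 34.0%.
- No device- or procedure-only subject and no death: the rate cannot rise above 30.0% through the CEC.

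**4. Two losses that must be kept apart.** Let s be the share of truly stimulation-related events recognised at the first call, and c the share of those that the CEC keeps. The tabulated share is s × c. With s = c = 0.8 it is 0.64. Of the 36 points lost, 20 (1 − 0.8) arise at the first call and 16 (0.80 − 0.64) at the CEC. Only the 16 points come from adjudication. The 20 would be lost with no committee at all. The CEC could recover such events only if it saw them.

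**The case against.** The case against is substantial, and most of its facts stand.

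- **The gate is generous.** A weak link that cannot be ruled out is possible, and possible counts as related. Unassessable cases default to possible. This protects doubtful cases, but not confident calls of unlikely or not related.
- **No event disappears.** All adverse events and serious adverse events are tabulated whatever their relatedness (Protocol 13.6, SAP 7.10), and an external data monitoring committee reviews accumulating safety data. What is at stake is the stimulation-related label.
- **Disagreements are disclosed.** CEC downgrades will be noted in the final report. That covers only events the CEC saw, and it does not alter the rates.
- **The CEC Charter is not among the documents.** It could widen referral. However, Protocol 12.2 and 11.5.1 themselves state the scope, and what 12.2 leaves to the Charter is member selection, meetings, roles, procedures and records.
- **Safety is descriptive.** No test of cDBS against aDBS is planned; the mode test compares the two adaptive modes. The tabulated rate is then itself the result.

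A reader might infer that adjudication can only lower the rate and never raise it. The documents do not support that. Deaths are referred regardless of relatedness, and an event called device- or procedure-related alone reaches the CEC and can be re-called stimulation-related.

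**Conclusion.** The asymmetry is real and can be read directly from Protocol 11.5.1 and 12.2. Non-fatal events called unrelated on all three axes are outside the committee's stated scope, while the committee's verdict sets the rates. The tendency is downward. The upward routes exist but look narrow.

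The size cannot be derived from the documents. The figures above rest on assumed counts and shares and show direction only.

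A reader might also infer a shortfall of 10% to 30%, or a distorted contrast between phases, and lay it at the CEC's door. For example, with an equal true rate of 20%, first-call recognition of 0.7 in one phase and 0.9 in the other gives 14% against 18%. That arithmetic describes under-recognition at the first call and would be the same without a committee. The documents give no evidence that calls differ by phase. The asymmetry applies to both phases alike unless they do.

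The point merits a change because the remedy is cheap and the outcome is the first safety item. It does not show that the planned safety analysis is invalid.

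**What to change.** 1. **Protocol 12.2 and 11.5.1:** send all serious adverse events to the CEC whatever the first relatedness call, with aDBS mode masked in the packet where feasible. Masking mode hides dual from single threshold; it does not hide cDBS from aDBS.
2. **SAP 7.10:** tabulate stimulation-related event rates by investigator determination and by CEC determination side by side, for the cDBS Baseline and aDBS Evaluation Phases. Keep the CEC rate as the planned one.
3. **State the remaining limit:** non-serious events called unrelated on all axes would still go unreviewed. Stimulation effects that resolve on reprogramming may often be of this kind.

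The first change recovers missed serious events. The second shows any net shift at the CEC but does not find missed events, so it does not replace the first. Counting an event as related on any single call is not needed: it would override the independent committee and still miss events that nobody called related.

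The cost is a few more CEC packets in a trial of about 40 treated subjects, one more table column, and possibly a slightly higher reported rate.
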